Abbreviations: CBC, complete blood count; CT, computerized tomography; EKG, electrocardiogram; MRI, magnetic resonance imaging; PSA, prostate-specific antigen; Mos, Month

1. All evaluations should be conducted within 30 days prior to registration/randomization. The exception to this is the radiologic evaluations and informed consent, which can be performed within 90 days prior to day 1.
2. CBC which includes WBC (with differential), platelets, Hgb, and Hct
3. Chemistries include albumin, alkaline phosphatase, total bilirubin, BUN, calcium, chloride, creatinine, glucose, sodium, potassium, total protein, SGOT [AST], and SGPT [ALT].
4. Those patients coming off study prior to PSA progression (i.e. for toxicity, etc.) should be evaluated for PSA levels every 3 months until PSA progression occurs.
5. ECGs may also be performed as clinically indicated throughout the study.
6. Radiologic evaluations (CT/MRI and bone scan) and chest x-ray (if applicable) should be conducted at PSA progression. Scans can also be obtained sooner as clinically indicated.
7. Quality-of-life (QoL) tools will include FACT-P, EORTC QLQ-C30/QLQ-PR25, and SHIM.
8. Patients should remain on study until PSA progression. This is defined as a PSA value ≥ 0.2 ng/mL above nadir that is confirmed by a second consecutive PSA value ≥ 8 weeks later which is higher (and ≥ 0.4 ng/mL). Patients should remain on study until the confirmatory PSA.
9. The total length of the study is 18 months for full enrollment and 24-months of follow-up for the last patient or 42 months. Patients who have 24-months of follow-up following treatment will continue to be followed for PSA determinations only and should remain on study until PSA progression or study end at month 42 whichever comes first.
10. To be conducted 2 months after the patient comes off study.
11. In patients who have consented, a tumor tissue block should be requested for banking, preferably from the prostatectomy specimen. If not available, a tissue block from the prostate biopsy should be submitted. In addition, a normal tissue block from the same patient (preferably from the prostatectomy) should be requested for banking. This only applies to the lead site (JHU).
12. Drug and diary review and dispensing may be done prior to or indicated day.
13. SRT to start 61 days (+/- 3 weeks) after Day 1. SRT will be delivered Monday-Friday
14. Decipher Test can be completed at any time before treatment ends on Day 180.

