5.2 Treatment Period

The following procedures are to be conducted each study visit on visit on Day 1, 61, 91, 120, 151 and 180 days while on study. Day 1, 61, 120 procedures should be done within seven days prior; day 91, 151 and 180 procedures should be done +/- 14 days (see Table 1):

- Review concurrent medications (see Appendix B for a listing of medications with the potential for drug interactions)
- Physical exam (vital signs, weight)
- ECOG performance status (Appendix A)
- Adverse events evaluation
- Review pill diary
- Laboratory tests (CBC w/diff, PSA, testosterone, comprehensive chemistry panel, including bilirubin, creatinine, SGOT[AST], SGPT[ALT])
- QoL questionnaires

The following procedures are to be conducted at each follow-up visit every 3 months ± 1 month up to 24 months (see Table 1). If participants are unable to return for follow-up, outside records may be obtained and assessments may be conducted via phone, email, or mail when possible:

- Review concurrent medications (see Appendix B for a listing of medications with the potential for drug interactions)
- Physical exam (vital signs, weight)
- ECOG performance status (Appendix A)
- Adverse events evaluation
- Laboratory tests (CBC w/diff, PSA, testosterone, comprehensive chemistry panel, including bilirubin, creatinine, SGOT[AST], SGPT[ALT])
- QoL questionnaires

The following procedure is to be conducted at each follow-up visit every 3 months ± 1 month past the first 24 months and up to 42 months (see Table 1):

- Laboratory test (PSA)

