Dose reduction for enzalutamide or placebo will be allowed. If a patient experiences a \geq Grade 3 toxicity or an intolerable side effect, withhold dosing for one week or until symptoms improve to \leq Grade 2, then resume at the same or a reduced dose (120 mg or 80 mg).

Any toxicity requiring enzalutamide discontinuation will be recorded as an AE in the subject's medical record and on the CRF.

5.4.1 *Seizures*

Seizures that occur at any time during the study, regardless of causality, severity, or outcome, will result in enzalutamide discontinuation and be recorded in the subject's medical record and on the CRF.

5.5 **End of Treatment/Treatment Discontinuation Visit (+/- 30 days from last dose)**

The following procedures are to be conducted every 3 months ± 1 month up to 24 months (see Table 1):

- Review concurrent medications (see Appendix B for a listing of medications with the potential for drug interactions)
- Physical exam (vital signs, weight)
- ECOG performance status (Appendix A)
- Adverse events evaluation
- Laboratory tests (CBC w/diff, PSA, testosterone, comprehensive chemistry panel, including bilirubin, creatinine, SGOT[AST], SGPT[ALT])
- QoL questionnaires
- Decipher Test (Will only be completed once before treatment ends on Day 180. This test will not be repeated.)

5.6 **Follow-up (Every 3 months for ≥ 24 months or until death)**

Patients will be followed for ≥ 2 years (and up to 42 months total) after removal from treatment or until death. Patients withdrawn from the study because of AEs will be followed until the adverse event has either resolved or stabilized. Reasons for premature withdrawal should be determined and noted.

Freedom-from-PSA-progression (FFPP) is the primary objective and is defined as the time from randomization to the date of PSA progression. A subject who does not have PSA progression at the time of the analysis will be censored at the last date of PSA measurement. In patients who achieve an undetectable PSA value (defined as ≤ 0.1 ng/mL), PSA progression is defined as a detectable PSA value (≥ 0.2 ng/mL) that is confirmed by a second consecutive PSA value obtained ≥ 8 weeks later which is higher (and ≥ 0.4 ng/mL). In patients who do not achieve an undetectable PSA, PSA progression is defined as a 0.2 ng/mL increase from nadir that is confirmed by a second consecutive PSA value obtained ≥ 8 weeks later which is higher.

5.7 **Concomitant Medications**

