10.1.2 Analysis of secondary endpoints

The first secondary endpoint is time to local recurrence within the radiation field, defined as the time from randomization to the date of local recurrence of disease. Subjects who do not have local recurrence will be censored on the date of their last evaluable tumor assessment for local recurrence. Subjects who start any subsequent anti-cancer therapy without a prior reported local recurrence will be censored at the last evaluable tumor assessment prior to initiation of the subsequent anti-cancer therapy.

The second secondary endpoint is metastasis free survival (MFS), defined as the time from randomization to the date of metastasis or death from any cause up to 90 days following the last response assessment, whichever occurs first. A subject who does not have metastasis and is alive will be censored at the last date of tumor assessment.

Time-to-event endpoints (time to local recurrence and MFS) will be analyzed similarly as described for the primary endpoint (FFPP).

Safety and tolerability will also be evaluated as secondary objectives. For safety analysis, overall safety profile and toleration of Arm A and Arm B will be characterized by type, frequency, severity, timing and relationship of study therapy of adverse events and laboratory abnormalities. Adverse events will be summarized by the frequency of patients experiencing treatment emergent adverse events corresponding to body systems and by worst NCI CTCAE (version 4.0) grade.

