10.3 Safety Analysis

10.3.1 Evaluation of adverse events

Treatment-emergent adverse events will be translated from investigator terms to MedDRA v6.0 terminology and summarized (number and percentage of patients) for all patients who receive at least 1 dose of enzalutamide. Adverse event summaries will be organized by body system, frequency of occurrence, intensity (ie, severity grade), and causality or attribution. Patients who experience an adverse event more than once will be counted only once. The occurrence with the maximum severity will be used to calculate intensity.

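### Adverse events are summarised only as crude patient percentages, and the plan contradicts itself on whether their follow-up stops at PSA progression; if it does, late-event percentages tilt modestly against enzalutamide

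*Combined protocol and SAP*

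**What the plan says.** **Summary measure.** The synopsis and sections 10.1.2 and 10.4.3 give the same summary: "Adverse events will be summarized by the frequency of patients experiencing treatment emergent adverse events corresponding to body systems", and by worst CTCAE grade. Section 10.3.1 makes it a number and percentage and adds: "Patients who experience an adverse event more than once will be counted only once". Section 10.1.2 says the safety profile will be "characterized by type, frequency, severity, timing and relationship of study therapy of adverse events and laboratory abnormalities", so timing is named, but no method is attached to it. The term treatment emergent is not defined.

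**Denominator.** Section 10.2.2 puts every man dosed with study medication in the safety population. Section 10.3.1 instead says "summarized (number and percentage of patients) for all patients who receive at least 1 dose of enzalutamide", which read literally leaves out Arm A.

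**What is recorded, and when.** Section 5.2.3 collects all AEs regardless of cause from registration to the post-treatment visit. After that it records only new treatment-related AEs and SAEs, plus seizures of any cause. AE evaluation is part of the follow-up visits in section 5.2: "The following procedures are to be conducted at each follow-up visit every 3 months ± 1 month up to 24 months". Section 5.5 lists the same schedule. Past 24 months only PSA is measured.

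**When a man leaves.** Footnote 8, attached to both follow-up columns of Table 1, says "Patients should remain on study until PSA progression" and "Patients should remain on study until the confirmatory PSA". Footnote 4 provides only PSA for men who come off study before progression. Section 5.6 says "Patients will be followed for ≥ 2 years (and up to 42 months total) after removal from treatment or until death", with no mention of progression.

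**The concern.** A crude percentage counts every treated man in the denominator for the whole period, whether or not anyone was still asking him about adverse events. That is harmless when the arms are observed for similar lengths of time. Under footnote 8, the length of observation depends on the primary endpoint, and the design expects PSA progression to come sooner in Arm A. Placebo patients would then be watched for late events for less time, and the shortfall would grow with the efficacy of enzalutamide. Late incidence would also be understated in both arms.

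Safety and tolerability are secondary objectives (sections 2.2 and 8.1.2), and the synopsis presents the trial as groundwork for phase III. A late-toxicity comparison that partly reflects observation time would be a poor input to that decision.

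**Working it through.** **Plan's own figures.** Section 10.4.1 gives 2-year FFPP of 60% and 80%, exponential event times, hazard ratio 0.44, 39 events, one-sided alpha 0.10 and 90% power.
- λ_A = −ln(0.6)/24 = 0.02128 per month; λ_B = −ln(0.8)/24 = 0.00930 per month; ratio 0.437.
- Schoenfeld: 4(1.2816 + 1.2816)²/(ln 0.44)² = 38.99, i.e. 39 events. The plan's figure reproduces, so the same hazards are used below.

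**Window.** Month 7 is 6 months of drug plus 30 days. Month 30 is 6 months of drug plus 24 months of AE visits.

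**Exit time.** Exit is d months after the first PSA rise. Confirmation comes at least 8 weeks later and visits are 3-monthly, so d is about 2 to 3. I also show d = 0 (exit at the first rise).

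**Observed months per man in months 7-30**, if AE follow-up stops at exit:

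[exp(−λ(7−d)) − exp(−λ(30−d))]/λ

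For d = 3:
- Arm A: (0.9184 − 0.5629)/0.02128 = 16.70
- Arm B: (0.9635 − 0.7780)/0.00930 = 19.95

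| Exit | Arm A | Arm B | A/B, months 7-30 | A/B, months 0-7 |
|---|---|---|---|---|
| 3 months after first rise | 16.70 | 19.95 | 0.84 | 0.99 |
| 2 months after first rise | 16.35 | 19.77 | 0.83 | 0.98 |
| At first rise | 15.67 | 19.40 | 0.81 | 0.96 |

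**Effect on a crude percentage.** The documents give no late-AE rate, so I assume the same constant hazard r in both arms from month 7. The true 23-month risk is 1 − exp(−23r). The expected crude proportion is

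p = r/(r+λ) × exp(−λ(7−d)) × [1 − exp(−23(r+λ))]

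For d = 3 and r = 0.01:
- Arm A: 0.3197 × 0.9184 × 0.5130 = 0.151
- Arm B: 0.5182 × 0.9635 × 0.3584 = 0.179

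| r per month | True late risk | Arm A | Arm B | Excess, points | Ratio | Men of 48 |
|---|---|---|---|---|---|---|
| 0.0022 | 5% | 3.6% | 4.3% | 0.7 | 1.19 | 0.3 |
| 0.005 | 10.9% | 7.9% | 9.4% | 1.5 | 1.19 | 0.7 |
| 0.01 | 20.5% | 15.1% | 17.9% | 2.8 | 1.19 | 1.4 |
| 0.02 | 36.9% | 27.3% | 32.2% | 5.0 | 1.18 | 2.4 |

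With d = 2 the ratio is 1.20-1.21. With d = 0 it is about 1.23, and the excess runs from 0.4 to 2.8 men.

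**Against sampling noise.** The standard error of the difference is √{[p_A(1−p_A) + p_B(1−p_B)]/48}. It is 4.0 points at a true risk of 5%, 7.6 points at 20.5% and 9.3 points at 36.9%. The expected excess is well inside one standard error throughout.

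**If AE follow-up continues past progression**, as sections 5.2, 5.5 and 5.6 read, progression does not shorten AE-observed time and this excess is zero.

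**The case against.** A reader might infer that men do leave AE follow-up at PSA progression, so the trial will report a spurious excess of late toxicity on enzalutamide. The documents do not support that.

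- **Exit at progression is not settled.** Section 5.6 follows men for at least 2 years after treatment, and sections 5.2 and 5.5 schedule AE visits to 24 months with no progression stop. On the other side, section 5.6 lists no AE procedures of its own, and nothing expressly schedules AE visits once a man has gone off study under footnote 8. The conflict is real and neither reading can be assumed.
- **The planned tables may not cover the late period.** Section 7.1.1 bounds an adverse event at 30 days post-treatment, and section 7.4.2 sets a reporting window of at least 30 days after radiotherapy. If treatment emergent carries that meaning, the crude tables cover a period in which observation is nearly equal. Because the plan does not say so, this limits the concern without removing it.
- **Late recording is narrow.** After the post-treatment visit, section 5.2.3 records only new treatment-related AEs and SAEs, plus seizures. This stands, and makes the higher assumed late risks less plausible.
- **The excess is small in absolute terms, and no AE hypothesis test is planned.** This also stands.

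None of this supplies a method for late events, which is the remaining gap.

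**Conclusion.** The point holds in a conditional form. The plan has no time-adjusted AE summary, leaves the treatment-emergent window undefined, and is inconsistent on whether AE follow-up outlasts PSA progression. If it ends at confirmed progression, Arm A has 16-17% less AE-observed time than Arm B in months 7-30 (19% less if men leave at the first rise). Equal late risks would then appear, in expectation, about 1.2 times higher on enzalutamide.

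This rests on exponential PSA progression from randomization at the planned rates, no other loss, a constant late-AE hazard that is equal between arms and unrelated to progression, and assumed late risks of 5-37%. It is a systematic tilt too small to be told from chance in 96 men. It is not a prediction that a false signal will appear.

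**What to change.** 1. **Reconcile** Table 1 footnote 8 with sections 5.2, 5.5 and 5.6, stating whether AE assessment continues after PSA progression.
2. **Define the window.** In sections 10.1.2, 10.3.1 and 10.4.3, restrict the crude number-and-percentage tables to AEs with onset from first dose through 30 days after last dose. Because section 5.4 lets a man stop study drug and complete radiotherapy, say which treatment's last dose is meant.
3. **Late events.** For recorded AEs with later onset, report by arm the cumulative incidence of first event, with death as a competing event, or events per person-month. End time at risk at each man's last AE assessment. Show AE-observed person-months per arm alongside.
4. **Denominator.** Align section 10.3.1 with the safety population in section 10.2.2 so that Arm A is included.

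Items 2 to 4 need SAP wording and one further table, with no new visits or patients, and the method in item 3 can be used under either reading of the follow-up rule. It needs AE onset and assessment dates. The visit-based AE forms in section 9.2.1 suggest these exist, but the CRF is not shown. The downside is that late-AE estimates will be imprecise with about 48 men per arm, and if follow-up ends at progression, censoring there assumes late-AE risk is unrelated to progression.

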10.2 Analysis Populations

10.2.1 Intent-to-treat/Response-to-treatment/Evaluable population

The Intent-to-Treat (ITT) Population includes all subjects who are randomized with study treatment assignment designated according to initial randomization. The ITT population will be the primary population for evaluating time-to-event efficacy endpoints (i.e. FFPP, time to local recurrence, MFS, and time to reinitiation of hormonal therapy) and patient characteristics.

Per Protocol Population will include all patients who are randomized and received at least one dose of study medication, and do not have any major protocol violations (for example, incorrect treatment group allocation according to randomization, not meeting the major inclusion/exclusion criteria for disease status and prior therapies, noncompliance to treatment plan or assessment schedule; additional concurrent prohibited therapies). The per-protocol analysis will serve as supportive.

10.2.2 Safety population

Safety Population will include all patients who receive at least one dose of study medication, with treatment assignments designated according to actual study treatment received. The safety analyses population will be the primary population for evaluating treatment administration/compliance and safety.

10.2.3 Special populations

10.2.3.1 Severe liver disease

Patients with baseline severe hepatic impairment (Child-Pugh C) are excluded from this clinical trial.

10.2.3.2 Lowered seizure threshold

In clinical studies, seizure was identified as a risk associated with enzalutamide treatment. In the controlled clinical Study CRPC2, seizures occurred in 0.9% (7/800) of patients receiving enzalutamide 160 mg daily, whereas no seizures occurred in patients treated with placebo. Confounding factors may have contributed to the occurrence of seizures in several of these cases. Dose appears to be an important predictor of seizure, with a greater risk of seizure at daily doses higher than 160 mg. In a dose escalation study involving 140 patients, no patients experienced seizures at or below daily doses of 240 mg, whereas 3 seizures were reported, 1 each at 360, 480 and 600 mg/day. Caution should be used in administering enzalutamide to patients with a history of seizures or other predisposing factors including, but not limited to, underlying brain injury, stroke, primary brain tumors or brain metastases or alcoholism. In addition, the risk of seizure may be increased in patients receiving concomitant medications that may lower the seizure threshold. Enzalutamide should be permanently discontinued in patients who have a seizure while on treatment.

10.3 Safety Analysis

10.3.1 Evaluation of adverse events

Treatment-emergent adverse events will be translated from investigator terms to MedDRA v6.0 terminology and summarized (number and percentage of patients) for all patients who receive at least 1 dose of enzalutamide. Adverse event summaries will be organized by body system, frequency of occurrence, intensity (ie, severity grade), and causality or attribution. Patients who experience an adverse event more than once will be counted only once. The occurrence with the maximum severity will be used to calculate intensity.

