7.3 Recording and Grading

7.3.1 *Recording*

All observed or volunteered adverse events, regardless of treatment group, severity, suspected causal relationship, expectedness, or seriousness will be documented.

A clinically significant change in a physical examination finding or an abnormal test result (ie, laboratory, x-ray, EKG) should be recorded as an AE, if it:

- is associated with accompanying symptoms
- requires additional diagnostic testing or medical or surgical intervention
- leads to a change in study dosing or discontinuation from the study
- requires additional concomitant drug treatment or other therapy, or
- is considered clinically significant by the investigator or ASMA

An abnormal test result that is subsequently determined to be in error does not require recording as an adverse event, even if it originally met one or more of the above criteria.

7.3.2 *Grading severity*

All adverse events will be graded for intensity on a scale of 0 to 5. Severity grades will be recorded and based on the most recent version of the NCI CTCAE handbook.

7.3.3 *Attributing causality*

After grading for severity, the investigator must evaluate all clinical AEs and abnormal laboratory values for possible causal relationship to enzalutamide. Causality attribution will be decided using the criteria outlined in Table 6.

Table 3 Relationship of Adverse Event to Study Drug

Relationship	Description
Unrelated	AE is clearly not related to enzalutamide
Unlikely	AE is doubtfully related to enzalutamide
Possible	AE may be related to enzalutamide
Probable	AE is likely related to enzalutamide
Definite	AE is clearly related to enzalutamide

Abnormal laboratory values of clinical significance that were present at baseline and did not change in severity or frequency during experimental therapy or intervention and those that can obviously be attributed to underlying disease will be recorded as unrelated and will not be considered when evaluating the AEs.

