10. STATISTICAL CONSIDERATIONS

10.1 Study Endpoints

10.1.1 *Analysis of the primary endpoint*

The study is a multi-center, double-blind, placebo controlled, randomized Phase II trial in patients with non-castrate PSA-recurrent prostate cancer after radical prostatectomy. Eligible patients will be randomized in a 1:1 ratio to one of two treatment arms: SRT *plus* placebo (Arm A) or SRT *plus* enzalutamide (Arm B). Randomization will be stratified by center, and surgical margin status (R0 vs R1), PSA prior to salvage treatment (PSA ≥ 0.5 vs < 0.5 ng/mL), and pathologic Gleason score (7 vs 8-10).

The primary objective of the study is to evaluate the efficacy of the two treatment regimens based on freedom-from-PSA-progression (FFPP). FFPP is defined as the time from randomization to the date of PSA progression. A subject who does not have PSA progression at the time of the analysis will be censored at the last date of PSA measurement. In patients who achieve an undetectable PSA value (defined as ≤ 0.1 ng/mL), PSA progression is defined as a detectable PSA value (≥ 0.2 ng/mL) that is confirmed by a second consecutive PSA value obtained ≥ 8 weeks later which is higher (and ≥ 0.4 ng/mL). In patients who do not achieve an undetectable PSA, PSA progression is defined as a 0.2 ng/mL increase from nadir that is confirmed by a second consecutive PSA value obtained ≥ 8 weeks later which is higher.

It is very unlikely deaths in the time frame of this trial will be from prostate cancer. Censoring the subjects that have died at the date of the last PSA measurement before death will be performed (as we will not know if PSA changes in the interval) unless there is clear evidence of death from prostate cancer per the treating physician and/or by autopsy.

FFPP will be summarized using Kaplan-Meier method by treatment arms. FFPP probability will be estimated using the Kaplan-Meier method. FFPP curves will also be displayed graphically. Differences in FFPP between treatment arms will be compared by the log rank test. The Cox proportional hazards regression model will be fitted, and the estimated hazard ratio (Arm B/Arm A) and corresponding 95% CI will be provided. Additionally, Cox regression models will be used to explore the potential influences of the other prognostic factors on the primary FFPP endpoints.

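### Section 10.3.1 defines the adverse event tables for enzalutamide recipients only, which contradicts the Safety Population in 10.2.2 and the two-arm safety summaries promised elsewhere

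*Combined protocol and SAP*

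**What the plan says.** Section 10.3.1 sets out how the adverse event tables are built. Treatment-emergent events are coded to MedDRA and given as counts and percentages "for all patients who receive at least 1 dose of enzalutamide". The tables are organized by body system, frequency, severity and attribution. A patient with repeated events counts once, at the maximum severity.

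Section 10.2.2 defines a different population: "Safety Population will include all patients who receive at least one dose of study medication", classified by the treatment actually received. It then gives that population its role: "The safety analyses population will be the primary population for evaluating treatment administration/compliance and safety".

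Section 10.1.2 commits to both arms: "overall safety profile and toleration of Arm A and Arm B will be characterized by type, frequency, severity, timing", with treatment-emergent events summarized by body system and worst CTCAE grade. The statistical method part of the synopsis and section 10.4.3 repeat that commitment.

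Section 7.3.1 requires documentation of events in both groups: "All observed or volunteered adverse events, regardless of treatment group".

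**The concern.** In a placebo-controlled trial, a man treated as assigned in Arm A never takes enzalutamide and so never meets the condition in 10.3.1. Anyone programming the adverse event tables would naturally work from that section. It is headed as the evaluation of adverse events, it is the only place that names the coding dictionary, it spells out the counting rule, and it ties the counts and percentages to a stated population. Followed to the letter, it produces a single column for enzalutamide recipients.

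The comparator column matters here because both arms also receive salvage radiation during the dosing period. Section 6.2.8 lists the expected radiation effects: bowel and rectal irritation, bladder complications and dermatitis. Events of this kind can be expected in both arms. A table of enzalutamide recipients alone cannot show how much of the observed toxicity would have occurred with radiation and placebo. Safety and tolerability is a stated secondary objective.

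**Working it through.** The plan gives no figure to reproduce on this point. The check sets the sections side by side and counts the planned denominators.

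**Who is in the safety tables, by section**

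- 10.3.1: patients with at least one dose of enzalutamide; placebo is not named.
- 10.2.2: patients with at least one dose of study medication, by treatment received; stated to be primary for safety.
- Synopsis, 10.1.2 and 10.4.3: Arm A and Arm B.
- 10.3.2 (serious events, withdrawals, deaths) and 10.3.3 (laboratory): no population named.
- 10.3.4 (exposure): all patients.
- 7.3.1 (recording, not analysis): events documented whatever the treatment group.

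Only 10.3.1 carries the restriction. No section says which text prevails. The content of the tables in 10.3.1 largely overlaps with that in 10.1.2 and 10.4.3 (treatment-emergent events, by body system, by worst grade), so these are conflicting population rules for much the same output. Nothing in 10.3.1 presents its table as an extra, enzalutamide-only display alongside a two-arm one.

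**Planned denominators**

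Inputs: 1:1 allocation (4.1.3); 96 patients, 48 per arm (10.4.1, new design). Assumption: every randomized man takes at least one dose of the product he was assigned.

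- 10.3.1 read literally: Arm A 0 + Arm B 48 = 48.
- 10.2.2: Arm A 48 + Arm B 48 = 96.
- Left out under 10.3.1: 96 − 48 = 48, and 48 / 96 = 50%.

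Men who are never dosed would lower both denominators. An Arm A man given enzalutamide in error would enter the 10.3.1 table, and would be classified with enzalutamide under 10.2.2 as well. Neither case changes the conclusion.

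The event count, power and significance level do not enter into this point.

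**The case against.** The strongest reply is that the two-arm safety analysis is already specified. Section 10.2.2 defines the governing population, and the synopsis, 10.1.2 and 10.4.3 each commit to both arms. Against these stands one phrase. This is right, and it limits the finding. A reader might infer from 10.3.1 that the trial abandons its controlled safety comparison, that no between-arm difference could be calculated, or that the safety objective has no controlled answer. The documents do not support any of these: events are recorded in both arms and summaries of both arms are promised in three places.

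A second reply is that enzalutamide here is shorthand for blinded study drug. The protocol does write that way elsewhere. The window for recording serious events in 7.1.2 runs from the last dose of enzalutamide, and causality in 7.3.3 is graded only against enzalutamide, although blinded staff cannot know who is taking it. The interruption rule names enzalutamide or placebo in 5.4 but only enzalutamide in 6.1.3. So deliberate exclusion of Arm A is the less likely reading. That remains an inference, however. In other places, such as 6.1.2.1, the protocol names both products when it means both, so a programmer cannot safely assume the shorthand.

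What stands after both replies is a stated table rule that conflicts with the plan's own safety population and has no text to resolve the conflict.

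**Conclusion.** The point holds as an internal contradiction. The population rule in 10.3.1 is wrong as written, because taken literally it removes Arm A from the adverse event tables that section defines. That is about 48 of 96 planned patients (50%), assuming each man takes at least one dose of his assigned product. The size applies to those tables only and depends on 10.3.1 being followed in preference to 10.2.2, a priority the documents do not give it. The plan as a whole keeps both arms in the safety analysis, and no data are lost. The correction should be made before the adverse event tables are programmed.

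**What to change.** In 10.3.1, replace the enzalutamide-only condition with: *for all patients in the Safety Population (at least one dose of enzalutamide or placebo), tabulated by treatment received*. State that the two arms are shown side by side, since both also receive salvage radiation. This brings 10.3.1 into line with 10.2.2, 10.1.2, 10.4.3 and the synopsis.

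The cost is one phrase in the analysis text. The data are already collected in both arms, and no clinical procedure, sample size or power figure changes. A between-arm difference with a confidence interval is not part of this correction: the plan treats safety descriptively, and adding one would be a matter of preference.
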